### **17.2 SERIOUS ADVERSE EVENTS (SAEs)**

SAEs are a subset of AEs that resulted in one of the following outcomes:

- Death;
- Life-threatening illness or injury (i.e. the patient was at risk of death at the time of the event; it does not refer to an event that hypothetically might have caused death if it were more severe);
- Inpatient hospitalization or prolongation of existing hospitalization;
- Persistent or significant disability or incapacity;
- A congenital anomaly or birth defect; or

- An important medical event (i.e. an event that jeopardize the patient or may require intervention to prevent one of the other outcomes listed above).

A serious adverse reaction (SAR) is any serious adverse event with a suspected causal relationship to the Study Drug. This means that there is at least reasonable evidence that the event might have been elicited by administration of the Study Drug.

### 17.3 CAUSALITY ASSESSMENT AND CLASSIFICATION

The PI must make a causality assessment for each adverse event experienced by a study subject following at least one dose of Study Drug (IP) according to the following guidance. However, any adverse event that occurs between written informed consent and administration of the first dose of IP will be considered a pre-treatment adverse event (PTAE), and this option should be selected in the applicable form rather than making a causality assessment.

- Certain: There is clear evidence to suggest a causal relationship and other possible contributing factors can be ruled out. The clinical event, including laboratory test abnormality, occurs in a plausible time relationship to IP administration and cannot be explained by concurrent disease or other drugs or chemicals. The response to withdrawal of the drug (de-challenge) should be clinically plausible. The event must be pharmacologically or phenomenologically definitive, with use of a satisfactory re-challenge procedure if necessary.
- Probable: There is evidence to suggest a causal relationship and the influence of other factors is unlikely. The clinical event, including an abnormal laboratory test, occurs within a reasonable time after administration of the Study Drug, is unlikely to be attributed to concurrent disease or other drugs or chemicals, and follows a clinically reasonable response on withdrawal (de-challenge). Re-challenge information is not required to fulfil this definition.
- Possible: There is some evidence to suggest a causal relationship; however, other factors may have contributed to the event (e.g. the subject's clinical condition, other concomitant treatments). The clinical event, including an abnormal laboratory test, occurs within a reasonable time after administration of Study Drug, but could be explained by concurrent disease or other drugs or chemicals. Information on drug withdrawal may be lacking or unclear.
- Unlikely: There is another reasonable explanation for the event occurrence. A clinical event, including an abnormal laboratory test, whose temporal relationship to Study Drug administration makes a causal relationship improbable, and which other drugs, chemicals or underlying disease provide plausible explanations.
- Not related: There is no evidence of any causal relationship between the clinical event and Study Drug administration, and/or sufficient information exists to indicate that the event is related to another etiology.

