### 3 LIST OF ABBREVIATIONS

AAP	American Academy of Pediatrics
ADR	Adverse Drug Reaction
AE	Adverse Event
ALCOA	Attributable, Legible, Contemporaneous, Original and Accurate
ATC	Anatomical Therapeutic Chemical
BW	Body Weight
CareCAT	Caregiver Administered Children's Acceptance Tool
CFR	Code of Federal Regulations
CH	Congenital Hypothyroidism
CMP	Clinical Monitoring Plan
CRO	Clinical Research Organization
CSR	Clinical Study Report
CTA	Clinical Trial Agreement
DMC	Data Monitoring Committee
DMP	Data Management Plan
DSU	Drug Safety Unit
eCRF	Electronic Case Report Forms
EDC	Electronic Data Capture
EOS	End of Study
EU	European Union
FAS	Full Analysis Set
FDA	Food and Drug Administration
FPFV	First Patient First Visit
FT4	Free Thyroxine
FU	Follow-Up
GCP	Good Clinical Practice
GI	Gastrointestinal
HR	Heart Rate
ICF	Informed Consent Form
ICH	International Conference of Harmonization
ID	Subject Identification
IND	Investigational New Drug
IP	Investigational Product (Study Drug)
IQ	Intellectual Quotient
IRB	Institutional Review Board
ISF	Investigator Site File
IWRS	Integrated Web Response System

LBW	Low Birth Weight
LPLV	Last Patient Last Visit
LT4	Levothyroxine
LOCF	Last Observation Carried Forward
MedDRA	Medical Dictionary for Regulatory Activities
NICU	Neonatal Intensive Care Unit
PI	Principle Investigator
PPI	Proton Pump Inhibitors
PPS	Per Protocol Set
PT	Preferred Term
PTAE	Pre-Treatment Adverse Event
SAE	Serious Adverse Event
SAF	Safety Analysis Set
SAP	Statistical Analysis Plan
SAR	Serious Adverse Reaction
SOC	Standard of Care
SOC (MedDRA)	System Organ Class
SOE	Schedule of Evaluations
SOP	Standard Operating Procedure
SUSAR	Suspected Unexpected Serious Adverse Reaction
T3	Triiodothyronine
T4	Thyroxine
TT4	Total Thyroxine
TFT	Thyroid Function Test
TH	Thyroid Hormone
TM	Telemedicine
TSH	Thyroid Stimulating Hormone
US	United States
USPI	United States Prescribing Information
VLBW	Very Low Birth Weight
WHO-DRL	World Health Organization – Drug Reference List

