## 13 TREATMENTS

### 13.1 STUDY DRUG (IP)

#### 13.1.1 DESCRIPTION OF STUDY DRUG

**Study Drug: Tirosint®-SOL (levothyroxine sodium) oral solution** (IBSA Pharma Inc.). Tirosint-SOL is a ready-to-use solution containing LT4. It is a clear, colorless to slightly yellow solution supplied in a 1 mL white, nontransparent, unit-dose ampule and is available in the following strengths (mcg/mL): 13, 25, 37.5, 44, 50, 62.5, 75, 88, 100, 112, 125, 137, 150, 175, 200. The inactive ingredients contained in the product are glycerol and water.

Tirosint®-SOL oral solution will be provided by the Sponsor at the following strengths: 13, 25, 37.5, 44, 50, 62.5, 75, 88, 100 mcg. This strengths range is considered sufficient based on the potential weight of the subjects enrolled in the study. However, additional strengths among those authorized for Tirosint®-SOL may be provided upon request in particular cases (e.g. obese subjects).

**Control: Crushed levothyroxine sodium tablets.** LT4 tablets will vary based on the Subject and SOC. Newly diagnosed neonates will start treatment with one of the FDA-approved LT4 tablets available on the market, as determined by SOC. Infants already on therapy will continue taking the same LT4 tablets that they are on as a prescription before inclusion in the study. Both branded and generic products will be allowed in the study, the choice being left to the PI.

Any change in source of the LT4, especially if not a standard brand, requires repeat TFTs (serum T4 and TSH) two to six weeks after the change to assess for the potential retitration of the dose ([AAP 2006](#), [Van Trotsenberg 2021](#), [Rose 2023](#)). This situation should be avoided when possible.

LT4 tablets are commercially available at the following strengths: 25, 50, 75, 88, 100, 112, 125, 137, 150, 175, 200, and 300 mcg. Inactive ingredients vary between formulations.

LT4 tablets will **NOT** be supplied by the Sponsor. Tablets will either be provided by the site hospital pharmacy or purchased by the parent/guardian of the subject at a local pharmacy and reimbursed. Any strength, among the commercially available ones, can be used in the study, though it is expected that the following strengths will most commonly be utilized: 25, 50, 75, 88, 100 mcg. If needed, tablets can be cut in halves to obtain the missing intermediate strengths, for example:

- 37.5 mcg daily dose will be obtained as half 75 mcg tablet;

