#### **15.3.2 TREATMENT COMPLIANCE**

Treatment compliance will be evaluated through the eDiary. Parents/guardians will indicate daily if the dose was effectively administered to the subject. The PI will review treatment compliance during the visits and in case of poor compliance will investigate reasons with the parents/guardians and instruct parents/ guardians about the importance of treatment adherence.

In addition, for Tirosint®-SOL the PI will count the returned unused IP. Significant discrepancies between IP count and eDiary records will need to be clarified with the parents/guardian during the visit and appropriately recorded.

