4 DEFINITIONS AND DATA CONVENTIONS

Body Mass Index (BMI)

BMI will be computed using the following formula:

$$\text{BMI} = \text{Body Weight (kg)} / (\text{Height (m)})^2$$

Daily dosage

Daily dosage (mcg) will be computed for each patient as:

$$\text{Daily Dosage} = \left(\frac{\sum_{i=1}^7 (\text{daily dosage}_i [\text{mcg}])}{7} \right)$$

where “i” is the day of the week.

Daily dosage/Body Weight

Daily dosage/Body Weight (mcg / kg) will be computed for each patient as:

$$\text{Daily Dosage/Body Weight} = \frac{\left(\frac{\sum_{i=1}^7 (\text{daily dosage}_i [\text{mcg}])}{7} \right)}{\text{Weight [kg]}}$$

where “i” is the day of the week.

Previous medications

Medications reported with an end date before the first study treatment administration (end date < date of first study treatment administration).

Concomitant medications

Medications reported as ongoing or with an end date after the first study treatment administration (ongoing or end date ≥ date of first study treatment administration). Any medications with an unknown end date will be assumed to be concomitant medications.

Treatment-Emergent Adverse Events (TEAEs)

Treatment-Emergent Adverse Events are defined as follows:

- Adverse events which started on or after the first study treatment administration.
- Adverse events without start date and with an end date after the first study treatment administration.
- Adverse events without start date and reported as ongoing (for subjects who take at least one dose of study treatment).

Pre-Treatment Adverse Events (PTAEs)

Adverse events which start before the first study treatment administration (start date < date of first study treatment administration).

Serious Adverse Events (SAEs)

Adverse Event assessed as serious.

Drug related Adverse Events

Adverse Events with a relationship to treatment reported as "Certain", "Probable" or "Possible".

Adverse events leading to discontinuation

Adverse Events leading to discontinuation is an AE with action taken equal to "Drug withdrawn".

Adverse events leading to death

Adverse Events leading to death is an AE with outcome equal to "Fatal".

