10.1 Tolerability parameters

10.1.1 Adverse Events

The total number and percentage of subjects with at least one Adverse Event (AE), treatment-emergent Adverse Event, serious Adverse Event, drug-related Adverse Event, Adverse Event leading to treatment discontinuation and Adverse Event leading to death will be summarized by treatment group.

The following summary tables by treatment group will also be provided:

- Adverse Events by System Organ Class (SOC) and Preferred Term (PT);
- Serious Adverse Events by System Organ Class (SOC) and Preferred Term (PT);
- Treatment-Emergent Adverse Events by System Organ Class (SOC) and Preferred Term (PT);
- Drug related Treatment-Emergent Adverse Events by System Organ Class (SOC) and Preferred Term (PT);

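### Causality grading in Protocol 17.1–17.3 is tied to a term used mostly for Tirosint-SOL, so Control grades may be missing or misdirected in the by-arm drug-related adverse event tables

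*Protocol*

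**What the plan says.** **The rule for sites.** Protocol 17.3 requires a causality assessment for events "following at least one dose of Study Drug (IP) according to the following guidance". It adds that "any adverse event that occurs between written informed consent and administration of the first dose of IP will be considered a pre-treatment adverse event"; the site then chooses the pre-treatment option and gives no causality grade. All five grades, from certain to not related, are worded against IP or Study Drug administration. Sections 17.1 and 17.2 define an adverse drug reaction and a serious adverse reaction against the Study Drug as well.

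**What the term covers.** The abbreviation list expands IP as "Investigational Product (Study Drug)" and names no product. Section 13.1.1 labels one product "Study Drug: Tirosint ® -SOL (levothyroxine sodium) oral solution" and lists the other as "Control: Crushed levothyroxine sodium tablets". Sections 10.2 and 10.3 set the study drug against the control treatment. Section 15.3.2 says that "for Tirosint®-SOL the PI will count the returned unused IP".

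**The analysis.** SAP 4 separates pre-treatment from treatment-emergent events by date, relative to the first study treatment administration. It defines drug-related events as "Adverse Events with a relationship to treatment reported as" certain, probable or possible. SAP 10.1.1 summarises them by treatment group, including a table of "Drug related Treatment-Emergent Adverse Events by System Organ Class (SOC) and Preferred Term (PT)". Protocol 19.3.4 likewise plans tables of events at least possibly related to study treatment.

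**The concern.** The drug-related tables need causality grades made on the same basis in both arms. The grades are created at the sites under 17.3, and that section does not mention the Control product. Nothing in either document says how causality is to be judged for tablets.

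Both arms take levothyroxine, so related events are possible in both. These are the only planned safety displays that attribute events to treatment. If Control events went ungraded at some or all sites, the tables would compare an assessed arm with a partly or wholly unassessed one. Tirosint-SOL would look worse than it should, and reactions to tablets would be hidden. If sites read the rule differently, the Control count would depend partly on which site enrolled the child.

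**Working it through.** The documents give no adverse event counts or rates, so there is no planned figure to reproduce. The check is mainly a comparison of wording.

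**1. Which sense of Study Drug or IP does the protocol use?**

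| Place in the protocol | Sense |
|---|---|
| Synopsis (Treatment) and 13.1.1: separate Study Drug and Control labels | Tirosint-SOL |
| 10.2 and 10.3: study drug set against control treatment | Tirosint-SOL |
| 13.2.3: IP handling and resupply; 15.3.2: count of returned IP | Tirosint-SOL |
| Heading of 13.1, under which tablets are also described | Both arms |
| Table 1 footnote c and 16.1: Day 1 of study drug administration includes children staying on tablets | Both arms |
| 13.2.3: plural study drugs, directly after supply to both arms | Both arms |
| 14.1: no replacement of withdrawn children who received IP; 17.4: stopping IP for severe events | No arm restriction |

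Usage is mixed. The narrow sense is common enough that a site could reasonably apply it to 17.3.

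**2. What happens to a Control event on, say, study day 100 under the narrow sense?**

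- The site selects the pre-treatment option: there is no grade.
- The site decides that neither rule applies, because no IP dose was ever given: there is no grade.
- The site grades the event anyway, using definitions worded against the Study Drug: the natural answer is not related, because the child never received that product.

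None of these routes gives a certain, probable or possible grade. Under the broad sense the event is graded against tablets and there is no problem.

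**3. Does the SAP repair it?** Only in part. The date rule in SAP 4 makes the event treatment-emergent whatever option the site ticked. Drug-related status, however, comes only from the reported grade. SAP 8 says that missing values are not replaced, and no rule covers a blank grade or a pre-treatment tick on an event after Day 1. Such an event would be counted as treatment-emergent and not drug-related.

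**4. Would the table show the problem?** SAP 3 reports 31 randomised children without the arm totals. At 2:1, about 31/3 ≈ 10 would be Control (assumption). If each has probability r of at least one truly related event, the chance of a genuine zero is (1 − r)^n:

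| Assumed r | n = 9 | n = 10 | n = 12 |
|---|---|---|---|
| 5% | 0.63 | 0.60 | 0.54 |
| 10% | 0.39 | 0.35 | 0.28 |
| 20% | 0.13 | 0.11 | 0.07 |
| 30% | 0.04 | 0.03 | 0.01 |

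For n = 10 and r = 10%, 0.90^10 = 0.35. At low rates, a zero made by the form could not be told from a zero by chance. The rates are assumed; neither document gives one.

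**The case against.** The strongest reply is that both arms were meant. Day 1 of study drug administration expressly includes children staying on tablets, and tablets are described under the Study Drug (IP) heading. Protocol 17.5 lists a causality assessment among the minimum content of the report form for all serious events, with no exemption for Control. Section 17.7 speaks of treatment-related events, and both 19.3.4 and the SAP refer to treatment and not to IP. This stands as evidence of intent. It does not settle how a site applied 17.3 to non-serious events.

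A reader might go further and infer that every Control event is pre-treatment by definition. That does not follow. The interval in 17.3 runs from consent to the first IP dose, and for a child never given IP it has no end point. Under the narrow reading the rule is undefined for that child.

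A reader might also expect a spurious significant difference between arms. Protocol 19.3.4 plans tests for children with any adverse or serious event, but only similar summary tables for related events, and SAP 10.1.1 plans no test. Nor do the documents support a high related-event rate. Under 15.1.1, abnormal thyroid tests are never recorded as adverse events. Under 15.2.3, thyroid signs and symptoms count only if judged clinically significant.

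Finally, rewording the protocol now cannot change grades already given. That is correct, and it is why the remedy rests mainly on the SAP and on data queries.

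**Conclusion.** The concern holds as a minor point. The site-level rule for causality does not reliably produce the Control grades that the planned by-arm tables need, and the SAP's date rule does not supply them. The Control drug-related count may be too low, possibly zero, or inconsistent between sites.

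It is tempting to read this as a guaranteed zero for tablets. The documents do not support that. They contain neither the adverse event form nor any event data, and they do not show which reading sites used. The size of any under-count is therefore unknown: from none, if sites graded Control events against tablets, to all Control-related events, if every site read 17.3 narrowly.

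The effect is confined to displays that use the causality grade. Summaries of all, treatment-emergent and serious events do not use it. Nor do summaries of events leading to discontinuation or death, which SAP 4 defines by action taken and by outcome. The figure of about 10 Control children assumes that the 31 randomised split close to 2:1.

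**What to change.** 1. **Protocol 17.1–17.3.** Replace the references to Study Drug (IP) and to the first dose of IP with the assigned study treatment (Tirosint-SOL or LT4 tablets) and the first study treatment administration (Day 1). With enrolment closed on 31 March 2024, this mainly puts the intended reading on record.
2. **SAP 4 and 10.1.1.** State that drug-related means related to the assigned LT4 product. Before analysis, query every Control event with onset on or after Day 1 that is marked pre-treatment or has no grade. Confirm that Control events graded not related were judged against the tablets. Report by arm the number of events from Day 1 onward that lack a valid grade.
3. **If grades cannot be recovered.** Print a not-assessed entry for Control in the drug-related tables, not 0.

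The cost is two wording changes and queries on the events of roughly 10 children, with no new patients or assessments. Late causality judgements in an open-label trial are weaker than contemporaneous ones, so queried grades should be identifiable in the listings. If the queries fail, the between-arm comparison of drug-related events is lost and the rest of the safety analysis stands.

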
#### 17.4 SEVERITY CLASSIFICATION

Regardless of the classification of an adverse event as serious or non-serious, the severity of an adverse event will be rated according to the following definitions:

- Mild: Symptom barely noticeable to subject and does not interfere with subject's daily activities. Minimal or no treatment typically needed for relief of symptom.
- Moderate: Symptom may cause some discomfort and may interfere with subject's daily activities. The subject can continue the study, even if treatment of symptom may be needed.
- Severe: Symptom causes severe discomfort and interrupts the subject's daily activities. They may be of such severity that IP administration has to be stopped and the subject may be treated for symptoms and/or hospitalized.

It should be noted that a severe adverse event does not have to be serious in nature and vice versa. Contrary to the other two classifications (seriousness and causality), the classification of severity does not have any impact on reporting procedures.

#### 17.5 REPORTING

All non-serious AEs experienced by a study subject from the time of written informed consent through EOS or discontinuation must be recorded in the source documents and eCRFs.

All SAEs experienced by a study subject from the time of consent signing through twenty-five (25) days (which is equivalent to 5 half-lives of LT4 in children (Colucci 2013)), post-discontinuation or intended follow-up period (EOS), must be recorded in the source documents and eCRF. Within 24 hours of discovery, the PI (or designee) should complete an initial form and submit to:

IBSA – Drug Safety Unit (DSU)

[REDACTED]

The initial form should contain at least the following information:

- Protocol number;
- Subject's study identifiers (screening and/or randomization number, age, sex);
- Relevant medical history and any concomitant medications taken during the study;
- SAE description and onset;
- Causality assessment;
- Study Drug and batch number;
- Date of initial dose and the last dose before onset of SAE;
- Detailed description of the circumstances leading to the SAE;

- Specific treatment of the SAE;
- Outcome;
- Principal investigator's name, address, phone number and email address; and
- The principal investigator's signature and date.

If applicable, the Investigator should also send to IBSA (upon anonymization):

- any examinations carried out to investigate the SAE;
- hospital discharge summary.

Missing information should not lead to a delay in reporting to IBSA. All effort should be made by the Investigator to obtain any useful information for the report of the SAE.

In case of death, the Investigator will be requested to forward the autopsy report, if available.

When additional information becomes available, the PI or designee will complete a follow-up form and submit it to the above entities within 48 hours.

Although a designee of the PI may collect information on the initial and follow-up form, the PI will review and sign and date the form(s) to attest to the accuracy and completeness of the information therein.

PIs are responsible for submitting any SAE that occurs to their local IRB, in accordance with the local IRB guidelines.

The Sponsor will review all SAEs to determine whether they meet the definition of a Suspected Unexpected Serious Adverse Reaction (SUSAR) using reference safety information in the IB and USPI, if applicable. In such instances, the Sponsor expects the PI or designee to expedite retrieval of necessary information on the subject and event. Sponsor will submit a safety report to FDA and participating PIs within 15 calendar days of the determining the event qualifies for expedited reporting. PIs will submit safety report to the IRB, as applicable within the appropriate timelines.

